15.11 Records and Reports

15.11.1 Investigator Records

At a minimum, the following records must be kept by the investigator:

- All essential study documents and correspondence that pertains to the clinical study
- CIP and, if applicable, any amendments
- User guide(s)
- Medtronic and IRB approved Subject ICF and assent form (if applicable)
- IRB and Regulatory authority approval or notification
- Fully signed clinical study agreements (i.e. including Form of Investigator Statement, Clinical Trial Agreement, Financial Disclosure and Confidential Disclosure Agreement)
- Completed Delegation of Authority Log
- Training documentation of all investigational center staff
- Subject Screening log and/or Subject ID log
- Signed, dated and fully executed Subject ICF and assent forms (if applicable)
- Source documentation
- Fully executed eCRFs and corrections
- Report of AEs and Device Deficiencies

Medtronic Business Restricted

- Device accountability records
- CIP Deviation/CIP Non-Compliance, if any
- Clinical Bulletins- A brief official update or summary of current study news on a matter of immediate interest and high importance to investigational center surrounding the CIP.
- Current signed and dated curriculum vitae (CV) of PI (and key study team members if required per local requirements)
- Study Reports

15.11.2 Investigator reporting responsibilities

Table 3. Investigator Reporting Responsibilities

Report	Submit to	Description/Constraints
AEs and Device Deficiencies	Sponsor, IRB, and regulatory authority, where applicable	Refer to Sections 11 for reporting requirements.
Withdrawal of IRB approval (either suspension or termination)	Sponsor	An investigator shall report to the sponsor, within 5 working days, a withdrawal of approval by the reviewing IRB of the investigator's part of an investigation.
Progress report	Sponsor and IRBs	The investigator must submit this report to the sponsor and IRB at regular intervals but in no event less than yearly.
Study deviations	Sponsor and IRBs	Notice of deviations from the CIP to protect the life or physical wellbeing of a subject in an emergency shall be given as soon as possible but no later than 5 working days after the emergency occurred.
Failure to obtain informed consent and assent prior to investigational device use	Sponsor and IRBs	If an investigator uses a device without obtaining informed consent and assent, the investigator shall report such use within 5 working days after device use.
Final report	Sponsor, IRBs and Regulatory Authorities (as applicable)	This report must be submitted within 3 months of study completion or termination of the investigation or the investigator's part of the investigation.
Other	Sponsor, IRB and FDA	An investigator shall, upon request by a reviewing IRB, FDA or any other regulatory agency, provide accurate, complete, and current information about any aspect of the investigation.

15.12 Record Retention

The sponsor and investigator will retain all records and documents pertaining to this study. They will be available for inspection by the appropriate regulatory agencies. In addition, the Investigator will retain the source documents from which the information entered on the eCRF was derived. These records are to be retained in a secure storage facility maintained by the investigational center until 2 years (or longer if local laws require) after approval of the above-listed study devices or termination of the study, whichever is longer. The Investigator should not dispose of these records without the approval of the sponsor.

15.13 Suspension or Early Termination

Sponsor or a Regulatory Authority may decide to suspend or prematurely terminate the clinical study (e.g. if information becomes available that the risk to study subject is higher than initially indicated, lack of enrollment or because of a business decision). If the clinical study is terminated prematurely or suspended, sponsor shall promptly inform the investigators of the termination or suspension and the reason(s) for this. The investigator shall then promptly inform the reviewing IRB and the study subjects.

15.14 Early Investigational Center Suspension or Termination

Sponsor, IRB or a Regulatory Authority may decide to suspend or prematurely terminate an investigational center (e.g., in case of expiring approval of the reviewing IRB, non-compliance to the CIP, or lack of enrollment). The suspended clinical studies cannot be resumed without permission from IRB. If an investigational center is suspended or prematurely terminated, sponsor shall promptly inform the investigator(s) of the termination or suspension and the reason(s) for this. The investigator shall then promptly inform the reviewing IRB and the study subjects.

When the risks are found to outweigh the potential benefits or when there is conclusive proof of definite outcomes, investigators must assess whether to continue, modify, or immediately stop the clinical study in the respective investigational center and immediately inform the sponsor and IRB, if applicable.

15.14.1 Subject Follow-up in Case of Termination

In case of early investigational center suspension or termination, all subjects should be contacted to plan an early Termination visit at the investigational center. All efforts will be made to complete and report all study observations at the time of termination. The subject will return the study devices to the investigational center.

15.15 Study Close Out

At the time of a study close-out, the investigators will be notified by sponsor. Appropriate notification/report to IRB and Regulatory Authority will be provided if required per local laws and

Medtronic Business Restricted

regulations.

17.2 Labeling and IFUs of Devices

The current labeling and IFU for the study devices will be provided to the investigators under separate cover.

17.3 Sample Consent Materials

Samples of the following consent forms/materials will be provided in a separate cover which includes the California Experimental Subject's Bill of Rights (if applicable), ICF and assent form, and the HIPAA Authorization.

Medtronic Business Restricted

18 Version History

Version	Summary of Changes	Author(s)/Title
A	Not Applicable, New Document.	[REDACTED]
B	
▪ Device updates
○ Added InPen Basal smart cap○ Removed CONTOUR NEXT LINK 2.4 study meter and DIABNEXT devices○ Updated Guardian Connect regulatory status○ Updated part numbers for several devices○ Updated Potential Risks (Section 10.1)▪ Updated "Version Date" year from 2020 to 2021 to correct version date of previous CIP version▪ Clarified subjects that are 13 years of age and older may do optional video injection site capture▪ Updated "weekly surveillance report" to "data surveillance report"▪ Updated visit activities table (Section 9.2)	[REDACTED]
C	
▪ Device updates
○ Added adapters○ BodyGuardian MINI▪ Updated study design to include optional BodyGuardian MINI cardiac monitoring▪ Updated sample size from 250 to 260▪ Updated exclusion criteria▪ Updated study visit schedule and visit schedule figure▪ Updated glossary (Section 1.1)▪ Updated list of trademarks (Section 1.2)▪ Updated Return or Disposal of Study Devices (Section 6.6.3)▪ Updated potential risks (Section 10.1)▪ Updated Investigational Centers and IRB (Section 17.1.1)▪ Updated CIP to match most current corporate CIP template▪ Typo/formatting corrections throughout document	[REDACTED]

Medtronic Business Restricted

## 1. Version History

Version	Summary of Changes	Author(s)/Title
1.0	• Not Applicable, New Document	[REDACTED]

## 2. List of Abbreviations and Definitions of Terms

Abbreviation	Definition
AE	Adverse Event
BMI	Body Mass Index
CGM	Continuous Glucose Monitoring
CIP	Clinical Investigation Plan
DKA	Diabetic Ketoacidosis
eCRF	Electronic Case Report Form
GCP	Good Clinical Practice

## 3. Introduction

In patients with insulin dependent diabetes mellitus, glycemic control is influenced by numerous factors, such as insulin dosage, insulin absorption, timing, physiological/lifestyle factors such as exercise, food intake, sleep, hormones and illness. These factors may contribute to significant variability in insulin requirements, which makes self-management of diabetes challenging.

Today, there are 55 million patients globally taking insulin through injections as compared to the 1 million administering insulin via pump therapy. Some of these patients will move to insulin pump therapy over the course of their lifetime, but the majority will continue using injections. Their rationale to continue with insulin injections include the following reasons:

- There is higher patient out-of-pocket cost associated with pump therapy;
- The physical experience of wearing a pump device is not appealing; and
- There has been growth in new therapy options available to injection users, such as CGM, smart pens, and decision support apps.

While CGM has greatly improved a patient's ability to get rapid and accurate glucose readings, patients are still required to make hundreds of decisions a day with little guidance on what to eat, what to dose, when to dose, and how to manage activities such as exercise. Without actionable therapy guidance, the following key needs remain unmet for these patients:

- Understanding how specific foods, physical activity, sleep patterns, and other routines affect their personal glucose levels;
- Recovering quickly from low and high glucose levels;

- Avoiding overnight lows;
- Optimizing physical exercise to stay in range; and
- Knowing exactly how much insulin to take, and when, at mealtime and throughout the day.

Due to the lack of guidance on the key needs listed above, multiple daily injections (MDI) patients on the current state of the art therapies spend an average of 45-51% of their time within a healthy glycemic range, known as Time in Range (TIR), which is well below the TIR outcomes for pump users. The overall goal of the Smart CGM system is to significantly improve TIR and quality of life (QOL) for injection-based insulin users by improving the user experience in three key areas:

- (1) Personalizing dosing recommendations that are tailored to the patient's own physiology, lifestyle, and diabetes state;
- (2) Providing holistic decision support to the user in point-of-care situations; and,
- (3) Reducing the burden of logging information relevant to diabetes management.

The Smart CGM system will accomplish this by providing the patient with intelligent automation, detection, insights, and recommendations that will enable them to achieve significantly improved TIR and QOL as an MDI user.

## **4. Study Objectives**

The primary objective of this feasibility study is to collect data to be used for development of Medtronic Diabetes and Cardiac Diagnostics devices and products.

## **5. Investigation Plan**

The study is a multi-center, prospective single-arm design without controls. All subjects will participate for a minimum of 90 days (Phase 1) and some subjects 18 years of age or older will participate for up to 9 months (Phase 2). All subjects will wear the Guardian Connect system (real-time continuous glucose monitoring (CGM)) continuously and use smart insulin pens or insulin pens with smart caps for multiple daily injections and continue their standard therapy throughout the duration of the study.

See CIP Section 5 for additional details on Study Design.

The purpose of this study is to collect sensor, insulin, sleep, activity and food/meal data for a minimum of 90 days of wear (Phase 1) and up to a maximum of 9 months of device wear (Phase 2) with optional insulin injection video capture and/or menstrual cycle tracking and/or cardiac monitoring in subjects with insulin requiring diabetes 2-80 years of age.

## **6. Determination of Sample Size**

Up to 500 subjects with insulin-requiring type 1 or type 2 diabetes age 2-80 who use multiple daily injections (MDI) insulin therapy will be enrolled.

## **7. Statistical Methods**

### **7.1 Study Subjects**

#### **7.1.1 Disposition of Subjects**

The number of subjects screened, enrolled, completed and withdrawn in the study will be presented. The reasons for subject's withdrawal will be summarized.

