Electronic device data will be collected from the study devices using CareLink Personal and the FoodPrint mobile app and Nutriño cloud. Each site should create a new CareLink Professional account to review subjects' CGM data. CareLink software uses TLS technology, which encrypts all data it stores (21 CFR Part 11 compliant). Wearables will be reset to factory settings at subject's end of study visit. Sponsor-provided smartphone and watch will be reset to factory settings after subject exits study and prior to device return to sponsor.

Throughout the study, both in Phase 1 and Phase 2, subjects will continually use the Guardian Connect system, track insulin delivery via the smart pen or pen caps, track sleep, track activity, and respond to prompts (as applicable). Subjects are instructed to use information from the Guardian Connect app in an adjunctive manner, per product labeling. The general study timeline of activities is as follows:

Phase 1

- Day 1-30

For 7 consecutive days during Days 8-27 (to ensure there is sufficient time for site to review surveillance report prior to Visit 4), each subject should log food consumption (meals, drinks and snacks) concurrent with CGM, sleep and activity tracking, and insulin delivery data collection. The subject is required to check a fasting SMBG using the study meter after a minimum of 8 hours of fasting for two mornings during the week they log their food.

- Day 31-90

Each subject should log food consumption for a minimum of 7 consecutive days per month.

Day 100 will be the EOS unless the subject is participating in Phase 2. If EOS, devices should be returned, wearables reset to factory settings, and subject's participation in the study will be completed.

Phase 2

- Day 91-280

Some subjects 18 years of age or older will continue to provide data for an additional 180 days based on adherence to study requirements demonstrated during Phase 1. Subject will be asked to log food consumption (meals, drinks and snacks) for a minimum of 7 consecutive days per month concurrent with CGM, sleep and activity tracking, and insulin delivery data collection. At End of Study (EOS, Day 280 (± 7 days)) devices should be returned, wearables reset to factory settings, and subject's participation in the study will be completed.

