 - Determine if subject will participate in Phase 2
 - If not participating in Phase 2, determine Day 90 when subject may stop data collection and schedule Visit 6 (EOS)
- Visit 6 (Office): Day 100 (± 7 days) after Visit 2.
 - If EOS:
 - Return study meter, transmitter, wearables, sponsor-provided smartphone and cardiac monitor (if applicable)
 - Wipe data off (perform factory reset) wearables
 - Administer EOS questionnaire

Note: EOS questionnaires will be administered to all subjects at the end of their participation in the study. This includes subjects who are terminated or who voluntarily discontinue participation in the study.
 - If moving onto Phase 2, see below.

Phase 2: Subjects participating in study for over 90 days (up to 9 months):

- Visit 6 Day 90 Follow-up (Office): Day 90 (± 14 days) after Visit 2.
 - Dispense study supplies.
 - Based on data surveillance reports as available (provided by sponsor), discuss subject compliance (e.g. meal logging, CGM use, sleep and insulin tracking etc.)
 - Discuss and determine target dates for completing one 7-day consecutive meal logging prior to Visit 7
- Visit 7 Day 120 Follow-up (Phone): Day 120 (± 14 days) after Visit 2.
 - Based on data surveillance reports as available (provided by sponsor), discuss subject compliance (e.g. meal logging, CGM use, sleep and insulin tracking etc.)
 - Discuss and determine target date for completing one 7-day consecutive meal logging

[figure not shown]
Medtronic Business Restricted

prior to Visit 8

- Visit 8 Day 150 Follow-up (Phone): Day 150 (± 14 days) after Visit 2.
 - Based on data surveillance reports as available (provided by sponsor), discuss subject compliance (e.g. meal logging, CGM use, sleep and insulin tracking etc.)
 - Discuss and determine target date for completing one 7-day consecutive meal logging prior to Visit 9
- Visit 9 Day 180 Follow-up (Office): Day 180 (± 14 days) after Visit 2.
 - Dispense study supplies.
 - Based on data surveillance reports as available (provided by sponsor), discuss subject compliance (e.g. meal logging, CGM use, sleep and insulin tracking etc.)
 - Discuss and determine target dates for completing one 7-day consecutive meal logging prior to Visit 10
- Visit 10 Day 210 Follow-up (Phone): Day 210 (± 14 days) after Visit 2.
 - Based on data surveillance reports as available (provided by sponsor), discuss subject compliance (e.g. meal logging, CGM use, sleep and insulin tracking etc.)

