 - Discuss and determine target date for completing one 7-day consecutive meal logging prior to Visit 11
- Visit 11 Day 240 Follow-up (Phone): Day 240 (± 14 days) after Visit 2.
 - Based on data surveillance reports as available (provided by sponsor), discuss subject compliance (e.g. meal logging, CGM use, sleep and insulin tracking etc.)
 - Discuss and determine target date for completing one 7-day consecutive meal logging prior to Visit 12
 - Determine date for Day 280 when subject may stop data collection and schedule Visit 12 (EOS)
- Visit 12 End of study (EOS) (Office): Day 280 (± 7 days) after Visit 2.
 - Administer EOS questionnaire
 - Note: EOS questionnaires will be administered to all subjects at the end of their participation in the study. This includes subjects who are terminated or who voluntarily discontinue participation in the study.*
 - Return study meter, transmitter, wearables and sponsor-provided smartphone
 - Wipe data off (perform factory reset) wearables

Medtronic Business Restricted

Figure 3. Study Visit Schedule for Phase 1 and Phase 2, 90 Days and 280 Days of Guardian Connect system Wear

Medtronic Business Restricted

9.2 Scheduled Follow-up Visit Windows for Phase 1 and Phase 2, Subjects Participating in Study for Over 90 Days and Up to 9 Months, Visit Activities

	Phase 1						Phase 2						
	Visit 1 (Office)	Visit 2 (Office)	Visit 3 (Phone)	Visit 4 (Office)	Visit 5 (Office or Phone)	Visit 6, EOS (Office)	Visit 6 (Office)	Visit 7 (Phone)	Visit 8 (Phone)	Visit 9 (Office)	Visit 10 (Phone)	Visit 11 (Phone)	Visit 12, EOS (Office)
Visit Window	Enrollment	Up to 14 Days After Visit 1	Day 10 (± 4 Days) After Visit 2	Day 30 (± 7 Days) After Visit 2	Day 60, Day 60 (± 7 Days) After Visit 2	Day 100 (± 7 Days) After Visit 2	Day 90, (± 14 Days) After Visit 2	Day 120 (± 14 Days) After Visit 2	Day 150 (± 14 Days) After Visit 2	Day 180 (± 14 Days) After Visit 2	Day 210 (± 14 Days) After Visit 2	Day 240 (± 14 Days) After Visit 2	Up to Day 280 (± 7 Days) After Visit 2
Visit Activities and Data Collection													
Obtain California Experimental Subject's Bill of Rights (if applicable), ICF and assent form (if applicable), and HIPAA form	x												
Assess subject eligibility to participate in the study.	x												
Measure subject height and weight Note: BMI will be calculated automatically in the study database, based on height and weight measurements entered.	x			x		x	x		x			x	

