### 7.9.2 Other descriptive Endpoints

- Summary of completed data collection/available data
- Summary of study questionnaire results

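### Does the SAP need a split by phase for subject disposition and the end-of-study questionnaire?

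*SAP*

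**What the plan says.** SAP section 5 describes Phase 1 (at least 90 days, all subjects) and Phase 2 (up to nine months, some adults). After that the SAP does not mention phase.

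- **Disposition.** SAP 7.1.1 and Protocol 13.2 say "The number of subjects screened, enrolled, completed and withdrawn in the study will be presented", followed by one summary of withdrawal reasons. Completion is not defined.
- **Questionnaire and data collection.** SAP 7.9.2 lists two other descriptive endpoints: "Summary of completed data collection/available data" and "Summary of study questionnaire results".
- **Timing of the EOS questionnaire.** Protocol 9.1.1 states "EOS questionnaires will be administered to all subjects at the end of their participation in the study", and adds that this covers subjects who stop early. Those who stop after Phase 1 exit at "Visit 6 (Office): Day 100 (± 7 days) after Visit 2". Those who go on attend "Visit 6 Day 90 Follow-up (Office): Day 90 (± 14 days) after Visit 2", whose activities include no questionnaire, and exit at "Visit 12 End of study (EOS) (Office): Day 280 (± 7 days) after Visit 2". A separate baseline questionnaire is given at Visit 1.
- **Who continues.** Protocol section 5 says some adults "will continue to provide data for an additional 180 days based on adherence to study requirements demonstrated during Phase 1". The heading above that sentence runs from Day 91 to Day 280.

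SAP 7.9.1 states that the analysis is descriptive, with no powered analysis and no hypothesis test.

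**The concern.** A single EOS questionnaire summary would combine people with about 100 days of device use, people with about 280 days, and early leavers. The 280-day group is also adults only and chosen for good adherence in Phase 1, so duration of use, age and adherence would be tangled together. Splitting by exit group removes the mixing of times, but the Day 100 column then lacks the adherent adults who went on. Neither layout gives an end-of-Phase-1 result for everyone who completed Phase 1.

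A single disposition table could likewise count a subject who gave 90 days of data and then left Phase 2 simply as withdrawn. The table would then understate how many subjects met the target of 260 completing 90 days. Finally, the length of Phase 2 appears inconsistent, which matters if data completeness is expressed against an expected number of days.

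**Working it through.** No sample size, power or error rate is in dispute, and the plan derives none, so there is no plan figure to reproduce. The checks are schedule arithmetic and a comparison of the text.

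**1. Questionnaire timing** (Protocol 9.1.1)

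- Phase 1 exit: 100 − 7 = 93 to 100 + 7 = 107.
- Phase 2 exit: 280 − 7 = 273 to 280 + 7 = 287.
- Separation: 280 − 100 = 180 days nominally; 273 − 107 = 166 at the least; 287 − 93 = 194 at the most.

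The two scheduled groups do not overlap. The exit visit (Visit 6, Visit 12 or early) therefore identifies the exit group without ambiguity.

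**2. What a questionnaire at the Phase 2 Visit 6 would give**

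- Window for continuers: 90 − 14 = 76 to 90 + 14 = 104.
- Window for those stopping: 93 to 107.
- Largest spread within one end-of-Phase-1 column: 107 − 76 = 31 days.

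Some continuers would answer before Day 90, that is, before finishing Phase 1. Adding the questionnaire at that visit would not by itself give a clean common timepoint. It would also need matching edits in the synopsis schedule and the Section 9.2 table.

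**3. Disposition**

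The documents give neither the number of continuers nor a Phase 2 dropout rate. As an assumption, let 20-60% of 260 Phase 1 completers continue, and 10-30% of those leave in Phase 2.

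- Continuers: 260 × 0.20 = 52 to 260 × 0.60 = 156.
- Phase 2 withdrawals: 52 × 0.10 = 5.2 to 156 × 0.30 = 46.8.
- Whole-study completed count, if Phase 2 leavers are excluded: 260 − 46.8 = 213.2 to 260 − 5.2 = 254.8, although all 260 reached 90 days.
- Share of Phase 1 completers with an EOS questionnaire near Day 100: 40-80%.

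The difference could be visible, but the information that resolves it is planned. Protocol 9.10 requires the reason for each withdrawal to be documented, Section 9.2 requires an exit form, and visits are timed from Visit 2. The 90-day count can also come from the data-collection summary in SAP 7.9.2.

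Pairing 500 with 260 gives (500 − 260)/500 = 48%, but this is not a Phase 1 loss rate. The 500 is a cap and the 260 a floor. Protocol 7.2 counts a subject as enrolled at consent, so the 240 would include screen failures who never wore a device.

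**4. Length of Phase 2**

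- An extra 180 days after Day 90: 90 + 180 = Day 270.
- Days 91 to 280 inclusive: 280 − 91 + 1 = 190 days.
- Difference: 10 days, or 10/190 = 5.3%.

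Nine calendar months are 273 to 276 days, which lies inside the Visit 12 window of 273 to 287. Protocol 5.1 describes participation as approximately 280 days. The Visit 11 text and the figure captions point to Day 280 for data collection itself, so the wording does conflict. However, time in range is reported as a percentage, not as a count against scheduled days, and SAP 7.9.2 fixes no expected-days denominator.

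**The case for a change.** The strongest case for a change is that the questionnaire point concerns data collection as well as tabulation. Once a continuer has passed Visit 6, no analysis can recover an end-of-Phase-1 answer, and SAP 7.4 imputes only partial dates and times. One more use of an existing questionnaire at an office visit already planned would be cheap. The groups also differ in age and adherence as well as time, so a comparison of Day 100 with Day 280 answers cannot be read as an effect of longer use.

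The factual part stands: continuers have no such answer, and that comparison would be confounded. It does not follow that something planned has been lost. The stated objective is to collect data for product development. The questionnaire is an other descriptive endpoint with no timepoint, and nothing calls for a result on all Phase 1 completers. The questionnaire's content is not in the documents, so one cannot judge whether 100 or 280 days of use would change the answers. An exit questionnaire given at exit is the design as written; a second administration is a preference.

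The undefined term for completion also stands as a gap in detail. The reading that the SAP will pool the phases, however, rests only on its silence. The pooling statement in SAP 7.3 concerns centers, and the synopsis heads its endpoints with both phases without saying whether they are combined.

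**Conclusion.** No change to the plan is needed. The schedule facts are right: scheduled EOS questionnaires come in two clusters nominally 180 days apart, continuers have none at the end of Phase 1, and neither SAP 7.1.1 nor 7.9.2 names a phase. In a single-arm descriptive study, the missing split is detail that an analyst would ordinarily supply: disposition and reasons by phase, and EOS answers by exit group with a note that continuers have none at the end of Phase 1. The data for this are already planned. An added questionnaire would bring no planned result closer, and with the present windows it would mix answers up to 31 days apart. The 180-day and 190-day wordings are a drafting slip that the sponsor can reconcile when the text is next revised; the 10 days change no planned summary.

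This rests on three assumptions: exit visit and reason are recorded as the protocol requires; the report does not present Day 100 against Day 280 answers as a trend over time; and no end-of-Phase-1 questionnaire result is wanted. If the sponsor does want one, the question becomes one of design and should be settled before continuers pass Visit 6.
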